##### **Modified Intention-to-Treat (mITT) set**

The mITT set will consist of all randomized patients who are treated with at least one dose of the study drug and have a baseline HbA1c assessment. The assignment of patients to treatment groups will be based on the planned randomised study drug at the time of randomisation.

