#### 7.2.2.2 Secondary analyses of the primary endpoint

##### *Sensitivity analysis*

In order to check the sensitivity of the primary analysis results to missing data handling or to premature treatment discontinuation, sensitivity analyses will be performed as follows.

Multiple imputation of HbA1c change from baseline after 24 weeks is planned for on- and off-treatment values for the three treatment groups individually. These analyses will be performed based on all randomised patients who have a baseline HbA1c measurement.

Missing on-treatment values will be imputed using Markov Chain Monte Carlo (MCMC) simulation and standard techniques. Missing off-treatment data will be imputed based on the observed off-treatment data by treatment group, providing at least 6 patients provide off-treatment data at Week 24 in each treatment group. If fewer than 6 patients per treatment group provide off-treatment data at Week 24, on-treatment information from the placebo group will be used as a basis for the imputation. The imputation model will include baseline HbA1c and the last on-treatment value. The analysis model will be an analysis of covariance (ANCOVA) model including treatment, background therapy, and continuous baseline HbA1c and baseline eGFR; a common treatment estimate will be derived based on Rubin's method.

The number of imputations will be set to 100 in order to ensure adequate efficiency and stability of estimation of missing data.

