4 CHANGES IN THE PLANNED ANALYSIS OF THE STUDY

There are no changes in this TSAP compared to the statistical methods described in the CTP.

Proprietary confidential information © 2021 Boehringer Ingelheim International GmbH or one or more of its affiliated companies

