A3.10	Treatment with protocol excluded systemic steroids or recent change in thyroid hormone dose	Exclusion criterion #16, #17 met	PPS
A3.11	Relevant alcohol or drug abuse and other conditions affecting study compliance	Exclusion criterion #18 met	PPS
A3.12	Any other clinical condition unsafe for participation that would jeopardise patient safety while participating in this clinical trial	Exclusion criterion #5, #22, #24, #25, #26 met	None
A3.13	Renal insufficiency or renal impairment (assessed by eCcR)	Exclusion criterion #19 met	PPS
A3.14	Known allergy or hypersensitivity to empagliflozin or other SGLT-2 inhibitors	Exclusion criterion #21 met	None

Proprietary confidential information © 2021 Boehringer Ingelheim International GmbH or one or more of its affiliated companies

Table 6.2 :1 Important protocol deviations (cont.)

IPD Code	IPD Category & brief description	Example/Comment	Exclude from which analysis set
A3.15	Women who are pregnant, nursing, or who plan to become pregnant while in the trial.	Exclusion criterion #27 met	None
B	Informed Consent		
B1	Informed consent not available/not done	Inclusion criterion #7 not met	All
B2	Informed consent too late	Date of informed consent not obtained prior to any study related procedure. Minimum requirement <= date of Visit 1/date of any study procedure	None
C	Trial medication and randomisation		
C1.01	No study medication taken	Patient randomised according to IRT system but no medication taken according to eCRF/IVRS	TS, mITT, PPS
C1.02	Incorrect trial medication taken	Wrong medication taken, i.e. eCRF kit number does not match kit number assigned by IVRS* [Needs unblinding to determine if kit was same medication as assigned or not – so, will be finally judged after DBL]	PPS
C2.01	Treated without randomisation	Patient treated according to eCRF, but not randomised according to IVRS	mITT, PPS
C3.01	Non-compliance with study drug intake	Overall study compliance outside 80% and 120% (exclusive) or study treatment compliance below 80% in the last visit interval before primary endpoint assessment. [Final decision at the DBL meeting based on medical judgement.]	PPS
C4.01	Medication code broken at site without just cause	Medication code was broken for no valid reason.	PPS
D	Concomitant medication		

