6.3 SUBJECT SETS ANALYSED

The following analysis sets will be defined for this trial.

- *Screened patients set (SCR):*

Proprietary confidential information © 2021 Boehringer Ingelheim International GmbH or one or more of its affiliated companies

This patient set includes all patients screened for the trial, with informed consent given and who completed at least one screening procedure at Visit 1.

- *Treated set (TS):*

This patient set includes all patients who are randomized and treated with at least one dose of study medication. The assignment of patients to treatment groups will be based on the actual first study medication intake in the double-blind treatment period. The TS is the basis for safety analyses.

- *Modified Intention-to-Treat (mITT) set:*

This patient set includes all randomized patients who are treated with at least one dose of the study medication and have a baseline HbA1c assessment and at least one on treatment HbA1c value. The assignment of patients to treatment groups will be based on the planned randomised study medication at the time of randomisation. The primary efficacy analysis will be performed on mITT set with patients who have a baseline HbA1c and at least one on treatment HbA1c measurement during randomized period.

- *Per-protocol set (PPS):*

This patient set includes all patients in the mITT set who do not have any important protocol deviations (iPDs) which can be expected to have a distorting influence on the assessment of the primary endpoint. iPDs are detailed in [Table 6.2:1](#).

In [Table 6.3:1](#) the data sets which are to be used for each category class of endpoint are illustrated.

Proprietary confidential information © 2021 Boehringer Ingelheim International GmbH or one or more of its affiliated companies

Table 6.3:1 Summary of which data sets will be used for which class of endpoints

[figure not shown]
Class of endpoint	Subject sets			
	SCR	TS	mITT	PPS
Disposition	OR			
Demographics		OR		
Baseline variables		OR		
Background total daily insulin dose/concomitant medications		OR		
Concomitant diagnoses/relevant medical history		OR		
Exposure/compliance		OR		
Primary endpoints			Primary analysis (OC) & Secondary analyses (MI, OC-AD)	OC
Secondary and further efficacy endpoints-continuous			OC, OR#	
Secondary and further efficacy endpoints-binary			NCF	
Subgroup analyses			OC	
Safety endpoints		OR		

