6.6.2 Methods of data selection

Original result (OR) analysis

Original result analysis implies the analysis of data exactly as observed. OR analysis will be performed on endpoints that are either not affected by patients' antidiabetic rescue medication use or if it is not meaningful to apply any imputation rule on them for replacing the missing values.

Observed cases (OC) analysis

For all efficacy endpoints, it is planned to analyse only the available data that were observed while patients were on treatment, i.e., excluding the missing data. In other words, OC analysis will be performed and missing data in this analysis will not be replaced.

For all efficacy endpoints, this OC-technique will set all values measured after antidiabetic rescue medication taken to missing (antidiabetic rescue medication as defined in [section 6.6.1](#)).

Observed cases analysis including data after treatment discontinuation and rescue therapy (OC-AD)

To mimic an intent-to-treat (ITT) analysis, post-treatment as well as post-rescue measurements may also be included. This will be done as a secondary analysis of the primary endpoint with OC as the imputation rule.

Non-completers considered failure (NCF)

For binary endpoints, like a treat to target response of $\text{HbA1c} < 7.0\%$, a conservative method to replace missing values is to consider them as "failures". Missing data due to early discontinuation per the completer definition will be replaced as "failure" (i.e. $\text{HbA1c} \geq 7.0\%$) up to the planned final visit to be reached by all patients. Values obtained after rescue medication was started are also replaced as "failure".

A multiple imputation (MI) approach will also be used as a sensitivity analysis for the primary endpoint. Further details can be found in [Section 7.4.2](#).

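### SAP Table 6.3:1 lists the multiple-imputation sensitivity analysis under mITT, but protocol 7.2.2.2 bases it on all randomised patients with a baseline HbA1c, and SAP 4 declares no change

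*SAP*

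**What the plan says.** **Protocol.** Section 7.2.2.2 introduces the MI analyses as a check on the "sensitivity of the primary analysis results to missing data handling or to premature treatment discontinuation". It then names their population: "These analyses will be performed based on all randomised patients who have a baseline" HbA1c measurement. Neither a dose nor a later HbA1c is required. The primary, effectiveness and supplementary analyses are instead placed on mITT, which section 7.2.1 defines as follows: "The mITT set will consist of all randomized patients who are treated with at least one dose of the study drug and have a baseline" HbA1c assessment.

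**SAP.** Table 6.3:1 has columns for four sets: SCR, TS, mITT and PPS. For the primary endpoint the mITT column reads "Primary analysis (OC) & Secondary analyses (MI, OC-AD"; the PPS column holds only the observed-case analysis. SAP 6.3 requires mITT patients to have taken at least one dose and to "have a baseline HbA1c assessment and at least one on treatment HbA1c value". Table 6.2:1, code C1.01 ("Patient randomised according to IRT system but no medication taken according to eCRF/IVRS"), removes untreated patients from TS, mITT and PPS.

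SAP 6.6.2 adds: "A multiple imputation (MI) approach will also be used as a sensitivity analysis for the primary endpoint". It sends the reader to section 7.4.2, which is not in the readable text. SAP 4 says: "There are no changes in this TSAP compared to the statistical methods described in the CTP".

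**The concern.** The two documents give the same analysis different populations, and the SAP does not declare a change. The protocol's choice looks deliberate, because three neighbouring analyses are put on mITT and MI is not.

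Two groups are in the protocol's MI population but outside the tabulated one:

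- patients randomised but never treated;
- patients treated but with no on-treatment HbA1c.

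Both groups also contribute nothing to the primary MMRM. A sensitivity analysis with the same exclusions cannot show whether those exclusions matter.

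The second group is possible in this trial. Protocol 6.1 allows Visits 4 to 7 to be remote, and HbA1c is not among the remote-visit assessments listed in Appendix 10.2. A patient with a remote Visit 4 who then stops and gives no end-of-treatment sample has no on-treatment value. If that patient attends at Week 24, an observed off-treatment endpoint would be dropped.

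**Working it through.** **1. The sets side by side**

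| Randomised patient with a baseline HbA1c who is | Protocol MI set | Protocol mITT | SAP mITT |
|---|---|---|---|
| untreated | in | out | out |
| treated, no on-treatment HbA1c | in | in | out |
| treated, at least one on-treatment HbA1c, later stopped or rescued | in | in | in |
| treated, completer | in | in | in |

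Restoring the protocol's wording of mITT would close the second row but not the first. The table's column assignment therefore needs its own correction.

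**2. The two possibilities for SAP 7.4.2**

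- If it follows Table 6.3:1, the SAP departs from protocol 7.2.2.2, and SAP 4 is wrong.
- If it names the protocol's population, Table 6.3:1 contradicts it.

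In both cases something in the SAP must be corrected.

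**3. The plan's sample size reproduces**

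Inputs from protocol 7.5: difference 0.62, SD 1.1, two-sided alpha 0.05, power 90%, censoring rate 8%, information content 0.4.

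- Two-sample t-test: the smallest n is 68 per arm, with power 90.4% (Table 7.5:1 gives 90.3%).
- Actual n: 68 / (1 − 0.08 × (1 − 0.4)) = 68 / 0.952 = 71.4, so 72 per arm and 216 in total.

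These concern the primary MMRM and do not depend on the MI population.

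**4. Size of the shift**

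The documents do not say how many patients will be untreated or lack an on-treatment HbA1c. Assume k = 1 to 3 of 72 per arm, with no treatment effect in those patients.

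- Share of an arm: 1/72 = 1.4% to 3/72 = 4.2%.
- Planned censoring: 0.08 × 72 = 5.76 per arm.
- Simple dilution: (k/72) × 0.62 = 0.009 for k = 1 and 0.026 for k = 3.

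A second illustration gives every censored patient zero effect. It counts the omitted patients among the 5.76.

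- All randomised: 0.62 × (72 − 5.76)/72 = 0.570.
- SAP mITT: 0.62 × (72 − 5.76)/(72 − k) = 0.578 (k = 1), 0.587 (k = 2), 0.595 (k = 3).
- Differences: 0.008, 0.016 and 0.025.

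The arithmetic limit is k = 5.76, giving 0.620 and a shift of 0.05. It requires every censored patient to have no on-treatment value, which conflicts with the plan's information content of 0.4. If each censored patient contributes between 0 and 1 of a completer and the mean is 0.4, at most 60% can contribute nothing: 0.6 × 5.76 = 3.5 per arm. At that value the shift is 0.62 × 66.24/68.544 − 0.570 = 0.03. This bound covers censored patients only; untreated patients may not be counted in the 8%.

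**5. Scale**

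The standard error of a difference is about 1.1 × √(2/68) = 0.19. A shift of 0.026 is about 0.14 of that.

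**The case against.** The strongest reply is that the controlling section cannot be read. Table 6.3:1 is a summary, and SAP 7.4.2 may state the right population. The protocol itself has no named randomised set and defines the MI population inline; 7.4.2 could do the same. This stands. A reader might infer that the SAP certainly runs MI on mITT, or that the protocol's population cannot be built from the SAP. Neither follows from the readable text. What remains is that the table conflicts with the protocol.

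The second reply is that few patients are affected. Protocol 6.2.2 has the first dose given on site as the last activity of Visit 3, so untreated patients should be rare. Early stoppers must return for an end-of-treatment visit within 7 days. Protocol 5.1 takes HbA1c at every visit except Visit 2. SAP Table 6.7:1 counts HbA1c as on-treatment for 7 days after the last dose, and Table 6.7:2 opens the first window on Day 2. A stopper who attends on time therefore qualifies for mITT. This also stands, and it supports a small number, though not zero.

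The third reply concerns what the check still does. It is tempting to say that it leaves out the patients it was designed for, or that its agreement with the primary result is built in. The documents do not support that. Patients who stop or are rescued after one on-treatment HbA1c remain in SAP mITT. Under protocol 7.2.2.2 their missing off-treatment values are imputed from observed off-treatment data, or from placebo on-treatment information if fewer than 6 patients per group provide such data. That differs from the missing-at-random MMRM.

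**Conclusion.** The inconsistency is real on the visible text and should be corrected, but it is limited. As tabulated, MI cannot test the exclusion of untreated patients or of those with no on-treatment HbA1c; it still tests the handling of most discontinued and rescued patients.

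The probable effect on the MI difference is about 0.01 to 0.03 HbA1c points. That rests on an assumed 1 to 3 patients per arm and on a placebo-like response in them; the documents give neither. Such a shift would not by itself be expected to change the reading of a planned difference of 0.62. The case for correction is that a prespecified sensitivity population differs between protocol and SAP while the SAP says nothing changed.

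**What to change.** Before unblinding:

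- In SAP Table 6.3:1, move MI out of the mITT column and assign it to all randomised patients with a baseline HbA1c, analysed as randomised. Define this as a set in SAP 6.3 or inline.
- Align SAP 7.4.2 with the table.
- State how patients with no on-treatment value are imputed, and which of the protocol's two routes (on-treatment or off-treatment) applies to them. The protocol's imputation model uses the last on-treatment value, which they lack. A model using baseline HbA1c only is one workable option; the documents do not dictate it.

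If the narrower set is intended, declare and justify it in SAP 4 instead.

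The cost is SAP wording and one more population flag. The sensitivity estimate may become slightly less favourable.

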6.5 POOLING OF CENTERS

This section is not applicable because center is not included in the statistical model.

6.6 HANDLING OF MISSING DATA AND OUTLIERS

Based on the different reasons of patients' data missing for different endpoints, various methods will be used to assess the impact of missing data on the efficacy endpoints of this trial, depending upon the type of the endpoint (see [Table 6.3:1](#)).

Proprietary confidential information © 2021 Boehringer Ingelheim International GmbH or one or more of its affiliated companies

6.6.1 Definition of rescue therapy for censoring

For some of the imputation methods defined below, values after first rescue medication will be set to missing. In this context, the following three situations are defined as use of rescue medication:

- Additional antidiabetic medication used for ≥ 7 consecutive days
- For insulin, a change of $>10\%$ (increase/decrease) from the last dose recorded prior to the baseline visit (Visit 3) taken for ≥ 7 days
- For OADs, a change in dose (increase/decrease) compared with the baseline dose for ≥ 7 consecutive days

This approach will be used when considering which data to exclude from the OC analyses.

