### 3.3.4.1 Discontinuation of trial treatment

An individual patient will discontinue trial treatment if:

- The patient wants to discontinue trial treatment, without the need to justify the decision.
- The patient has repeatedly shown to be non-compliant with important trial procedures and, in the opinion of both, the investigator and sponsor representative, is not willing or able to adhere to the trial requirements in the future.
- The patient needs to take concomitant medication that interferes with the investigational medicinal product or other trial treatment. You may refer to [Sections 4.2.1](#) and [4.2.2](#).
- Introduction of rescue therapy due to hyperglycemia as described in section 4.2.1 does not lead to sufficient treatment efficacy (rescue criteria still met). In this case, the reason for discontinuation will be classified as “lack of efficacy”.
- Occurrence of hypoglycemia that may put the patient at risk with continued participation (e.g. repeated hypoglycemic episodes).
- DKA that may put the patient at risk with continued participation. Patients should be assessed for ketoacidosis immediately if symptoms occur, regardless of blood glucose level. Discontinuation or temporary interruption of study medication should be considered, until the situation is clarified.
- The patient can no longer receive trial treatment for medical reasons (such as surgery, adverse events, other diseases, or pregnancy). In case of a temporary reason, trial treatment should be restarted if medically justified.
- The patient experiences an infection with SARS-CoV-2. The patient may resume trial treatment following recovery from SARS-CoV-2 infection if the patient is expected to derive clinical benefit, as agreed between the investigator and sponsor.

Patients who discontinue treatment prematurely will be followed up until the end of the trial as outlined in the [Flow Chart](#) and [Section 6.2.2](#).

If a patient becomes pregnant during the trial the investigational drug will be stopped, the patient will be discontinued from the trial and the patient will be followed up until birth or otherwise termination of the pregnancy.

A patient can be discontinued from the trial after discussion between the sponsor and the investigator if the eligibility criteria are being violated.

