## 4.2 OTHER TREATMENTS, EMERGENCY PROCEDURES, RESTRICTIONS

### 4.2.1 Other treatments and emergency procedures

Throughout the duration of the trial, patients should continue to take insulin alone or in combination with acceptable OADs as background therapy.

Acceptable basal insulins should have duration of action up to 24 h such as insulin degludec, insulin glargin, insulin detemir or NPH (neutral protamine hagedorn) insulin. The background medication of OADs should remain unchanged throughout the study. Acceptable pre-mixed insulins could be once or twice daily posology only. The total prescribed insulin dose should not be changed by more than 10% of the baseline value in the 24 weeks after randomisation unless rescue therapy criteria for treatment of hyperglycemia are met or in case of hypoglycemia requiring insulin dose reduction beyond the defined limits. The background medication will not be provided as part of the clinical trial supplies.

The patients can take their background medication as they are used to and should have the same habits of dosing throughout the trial, where it is suggested that basal insulin is always given in the evening. Morning dose of OADs/any permitted pre-mixed insulin and study medication should be taken after the visits blood sample taken.

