### **7.3 HANDLING OF MISSING DATA**

For the analysis of the primary endpoint, the handling of missing data is described in [section 7.2.2.](#)

For percentage of patients with  $\text{HbA}_{1c} < 7.0\%$  after 24 weeks of treatment, the missing data will not be imputed. Patients who prematurely discontinue the treatment or initiate rescue therapy will be treated as non-responder (i.e.,  $\text{HbA}_{1c} \geq 7.0\%$  after 24 weeks of treatment).

No imputation for missing data will be performed for secondary efficacy endpoints of change from baseline in body weight, SBP, DBP and FPG. The missing data will be handled by MMRM model based on a likelihood method under the "missing at random" assumption.

Baseline Observation Carried Forward (BOCF) approach will be used for 2-hour PPG in ANCOVA analysis.

Missing or incomplete AE date will be imputed according to BI standards. Other missing safety data will not be imputed.

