7.5.2.1 Responder analysis

The HbA1c responder analyses will be performed on mITT (NCF) by determining the percentage of patients that fulfil responder criteria (for the definition of treat to target and relative efficacy response, see [Section 5.2.2](#)) by treatment. Non-completers considered failures (NCF) imputation-technique will be used to impute the missing data for this analysis strategy.

Each analysis will consist of a tabulation by treatment of the percentage of patients meeting the response criteria along with 95% exact confidence intervals for the percentage. Additionally, a logistic regression model with treatment, background therapy, baseline eGFR and continuous HbA1c will be fitted on the binary response variable to calculate the estimate of the odds ratio of each dose to placebo. Estimate of odds ratios and 95% confidence intervals (Wald) will be presented along with the p-values for each comparison.

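### The SAP counts insulin and OAD dose decreases as rescue, so a patient on study drug who reaches HbA1c below 7.0% after such a decrease is scored a non-responder, which the protocol does not call for

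*SAP*

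**What the plan says.** SAP 6.6.1 lists three situations that count as use of rescue medication:

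- an additional antidiabetic drug for at least 7 consecutive days;
- an insulin change of more than 10%, qualified as "increase/decrease) from the last dose recorded prior to the baseline visit (Visit 3) taken for" at least 7 days;
- an OAD dose change from baseline, up or down, for at least 7 consecutive days.

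No reason for the change is required.

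SAP 6.6.2 then says of NCF: "Values obtained after rescue medication was started are also replaced as" failure. SAP 7.5.2.1 applies NCF to the HbA1c responder endpoint: "imputation-technique will be used to impute the missing data for this analysis strategy". The analysis that keeps data after discontinuation and rescue (OC-AD) is limited to the primary endpoint: "This will be done as a secondary analysis of the primary endpoint with OC as the imputation rule". SAP Section 4 states: "There are no changes in this TSAP compared to the statistical methods described in the CTP".

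Protocol 7.3 gives the responder rule: "Patients who prematurely discontinue the treatment or initiate rescue therapy will be treated as non-responder". Protocol 3.3.4.1 describes rescue in terms of hyperglycaemia: "Introduction of rescue therapy due to hyperglycemia as described in section 4.2.1 does not lead to sufficient treatment efficacy". Protocol 4.2.1 limits insulin changes to 10% with two separate exceptions. One is that the hyperglycaemia rescue criteria are met; the other is "in case of hypoglycemia requiring insulin dose reduction beyond the defined limits".

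**The concern.** The responder endpoint should count patients who reach HbA1c below 7.0%. Under the SAP rule, a patient who reaches that target on study drug while needing less insulin or less OAD is recorded as not reaching it. This overwrites an observed success; it does not handle a missing value.

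Reductions may also differ by arm. The risk table in Protocol 1.4.2 says hypoglycaemia may be more frequent with empagliflozin plus insulin than with insulin alone. Protocol 4.2.1 makes insulin the first background drug to reduce. The documents give no rates, so neither the size nor the direction of the effect is known in advance.

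The same definition governs observed-case (OC) censoring in the primary MMRM. There the patient's values after the change are set to missing, earlier values stay, and the patient remains in the mITT set.

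**Working it through.** **Step 1. Compare the texts.**

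| Question | Protocol | SAP |
|---|---|---|
| What prompts rescue? | Hyperglycaemia, with confirmed FPG criteria (3.3.4.1; 4.2.1, Hyperglycemia) | Any reason (6.6.1) |
| Is an insulin reduction for hypoglycaemia rescue? | Listed as a separate exception to the 10% limit (4.2.1) | Yes, if more than 10% for at least 7 days (6.6.1) |
| Are rescue and background therapy distinct? | Yes; ongoing rescue is to be reduced before background therapy (4.2.1, Hypoglycemia) | A qualifying background change is itself rescue (6.6.1) |
| Who is a non-responder regardless of the observed value? | Patients who discontinue treatment or initiate rescue (7.3) | Early discontinuation, or values after rescue (6.6.2, 7.5.2.1) |

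The NCF sentence does not cite 6.6.1. However, 6.6.1 introduces its definition for some of the imputation methods that follow it, NCF is one of those, and the available SAP text has no other definition of rescue.

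**Step 2. Reproduce the plan's own figure.** Protocol 7.5 assumes a difference of 0.62, SD 1.1, two-sided alpha 0.05, 8% censoring and information content 0.4. A two-sample t-test for 90% power needs 67.1 per arm, so 68. Then 68 / (1 − 0.08 × 0.6) = 71.4, so 72 per arm. Power at 68 is 90.4% (stated: 90.3%).

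**Step 3. Size for the responder endpoint.** From the documents alone, one miscoded patient costs 1/72 = 1.39 percentage points in that arm.

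Everything else in this step is assumed: true response 30% on active and 12% on placebo, and 30% to 60% of reducers below 7.0%. The formula is: observed rate = true rate − (reduction rate × share of reducers below 7.0%). Power uses the two-proportion normal approximation with pooled null variance, 72 per arm, two-sided 0.05, without covariates.

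| Reductions, active / placebo | Share below 7.0% | Observed rates | Odds ratio | Power |
|---|---|---|---|---|
| none | – | 30.0% / 12.0% | 3.14 | 76% |
| 5% / 2% | 0.3 | 28.5% / 11.4% | 3.10 | 73% |
| 5% / 2% | 0.6 | 27.0% / 10.8% | 3.05 | 70% |
| 10% / 3% | 0.3 | 27.0% / 11.1% | 2.96 | 68% |
| 10% / 3% | 0.6 | 24.0% / 10.2% | 2.78 | 60% |
| 5% / 5% | 0.3 | 28.5% / 10.5% | 3.40 | not computed |
| 5% / 5% | 0.6 | 27.0% / 9.0% | 3.74 | not computed |

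In the 5% / 5% rows the difference in rates stays at 18 points, but the odds ratio rises.

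For small numbers of miscoded patients, the odds ratio falls only if miscoded responders on active exceed those on placebo by the ratio pA(1 − pA) / [pP(1 − pP)], where pA and pP are the true response rates. At 30/12 this is 0.21 / 0.1056 = 1.99; at 25/10 it is 2.08 and at 35/15 it is 1.78.

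**Step 4. Size for the primary endpoint.** Effective n = 72 × (1 − CR × 0.6), rounded down, where CR is the censoring rate; standardised effect 0.62/1.1; noncentral t.

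| Censoring rate | Effective n | Power |
|---|---|---|
| 8% (plan) | 68 | 90.4% |
| 13% | 66 | 89.5% |
| 18% | 64 | 88.6% |
| 28% | 59 | 85.9% |

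**The case against.** Five points can be made for the SAP.

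1. **The link to NCF is inferred.** SAP 6.6.1 closes by naming only the OC analyses, and the NCF paragraph does not refer back to it. This is true. If another meaning of rescue was intended for NCF, the SAP still needs to state it.

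2. **The published SAP is incomplete.** Its contents list skips sections, and the text refers to 7.4.2, which is not shown. A relieving analysis could be there. That caveat stands: the conclusion rests on the text available.

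3. **The protocol has no formal definition of rescue.** It speaks of adjusting insulin, caps changes in both directions at 10%, and in 7.2.3 leaves detail of the secondary analyses to the SAP. A two-way rule can therefore be read as putting stable background therapy into practice. This has weight for censoring in the primary model. It does not extend to scoring an observed HbA1c below 7.0% as a failure after an event that the protocol keeps separate from rescue.

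4. **The responder scenarios are assumptions.** At 5% / 2%, about 1 to 2 active patients and fewer than 1 placebo patient are miscoded (72 × 0.05 × 0.3 = 1.1 to 72 × 0.05 × 0.6 = 2.2; 72 × 0.02 × 0.3 = 0.4 to 72 × 0.02 × 0.6 = 0.9). The rise in the odds ratio at 5% / 5% needs the same share of reducers below 7.0% in both arms. If reducers respond at their own arm's rate, the observed rates are 30% × 0.95 = 28.5% and 12% × 0.95 = 11.4%, and the odds ratio is 3.10, a slight fall. This stands, and direction is therefore left open.

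5. **A rescue flag limited to increases still departs from the protocol**, because it does not require FPG confirmation. This also stands and should be declared.

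**Conclusion.** The concern holds. As written, the SAP classes qualifying dose decreases as rescue, and on the natural reading of its NCF rule it scores an observed success after such a decrease as a failure. The protocol does not call for this, and the SAP does not declare it.

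The only size that the documents fix is 1.4 percentage points per miscoded patient in an arm of 72. Under the assumed rates, the odds ratio moves from 3.14 to between 2.78 and 3.74. The difference in response shrinks if miscoded responders are commoner on empagliflozin. The odds ratio is inflated if they are about equally common in both arms.

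For the primary MMRM the direction of any bias cannot be determined, and the power cost is modest: 89.5% to 85.9% for 5 to 20 extra points of censoring, against 90.4%. Two-way censoring is defensible there given the stable-insulin objective, but it should be declared. The responder endpoint is secondary and outside the testing hierarchy, so the primary claim is not threatened. This should be fixed before unblinding.

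**What to change.** Before unblinding, replace the single definition in SAP 6.6.1 with two analysis flags:

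- **Rescue:** an added antidiabetic drug for at least 7 consecutive days, or an insulin increase of more than 10% or an OAD dose increase of the durations already stated.
- **Background reduction:** an insulin decrease of more than 10% or an OAD dose decrease of the durations already stated.

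Then:

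1. For NCF, count only the rescue flag and early discontinuation as failure. For patients with only the reduction flag, use the observed Week 24 HbA1c. Run the present two-way rule as a sensitivity analysis.
2. For the primary MMRM, choose one of two options. Either censor on the rescue flag only, or keep two-way censoring, declare it in SAP Section 4, and add a sensitivity analysis that restores post-reduction values only. OC-AD cannot serve for this, because it also restores values after discontinuation and after dose increases.
3. State in Section 4 that the rescue flag does not require the protocol's FPG confirmation.
4. State which flag defines the rescue counts and time to first rescue (Table 6.3:1 footnote) and the hypoglycaemia summary by rescue use (7.5.2.4). At present, a reduction made because of hypoglycaemia could itself count as rescue there.

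The cost is SAP wording, one derived flag and one or two extra runs. Changes in concomitant therapy are already recorded (Flow Chart; Protocol 8.3.1). Changing the primary censoring rule would slightly change what the primary analysis estimates; declaring and testing it avoids that. Patient management is unaffected.
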